LVEF Changes: If any of the following circumstances occur, the event(s) must be reported via CTEP-AERS within 7 calendar days

- Asymptomatic: Absolute decrease of >10% in LVEF compared to baseline and ejection fraction below the institution's LLN that does not resolve within 4 weeks (i.e.: defined as LVEF \geq LLN and absolute decrease \leq 10% compared to baseline)
- Symptomatic: Grade 3-4 LVEF

Please refer to the dose modification instructions for further information regarding Treatment Modification and Management Guidelines for LVEF Decrease.

Visual Changes: If RPED (retinal pigment epithelial detachments) is suspected or diagnosed or RVO (retinal vein occlusion) is diagnosed, the event(s) must be reported via

CTEP-AERS within 7 calendar days. Please refer to the dose modification instructions for further information regarding Treatment Modification and Management Guidelines for Visual Changes.

Pyrexia: Any occurrence of pyrexia accompanied by hypotension, or dehydration requiring IV fluids, or severe rigors/chills in the absence of an obvious infectious must be reported via CTEP-AERS within 7 calendar days.

Liver Chemistry Changes: If any of the following circumstances occur, the event(s) must be reported via CTEP-AERS within 7 calendar days

- ALT \geq 3xULN and bilirubin \geq 2x ULN or $>$ 35% direct bilirubin
- ALT \geq 3xULN and INR \geq 1.5, if INR measured (INR threshold does not apply if patient is on anticoagulant)
- ALT $>$ 5xULN
- ALT $>$ 3xULN persistent for $>$ 4 weeks
- ALT $>$ 3xULN associated with symptoms (new or worsening) believed to be related to liver injury or hypersensitivity

Please refer to the dose modification instructions for further information regarding Treatment Modification and Management Guidelines for Liver Chemistry Changes.

c. NOTE: All adverse events meeting the criteria in this table that occurs while the patient is on study treatment and for 30 days after the last dose of protocol treatment must be reported in CTEP-AERs according to the timeframes outlined. Any adverse event meeting the criteria that occurs more than 30 days after the last dose of protocol treatment and is related to Hydroxychloroquine/Placebo must be reported in CTEP-AERS according to the timeframes outlined.

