VASCULAR DISORDERS		
	Hypertension	
	Thromboembolic event ¹²	
	Vascular disorders - Other (hemorrhage) ¹³	

¹ This table will be updated as the toxicity profile of the agent is revised. Updates will be distributed to all Principal Investigators at the time of revision. The current version can be obtained by contacting [contact]. Your name, the name of the investigator, the protocol and the agent should be included in the e-mail.

² The incidence of anemia is increased when dabrafenib mesylate (GSK2118436B) is used in combination with trametinib dimethyl sulfoxide (GSK1120212B).

³ The frequencies of these events are based upon laboratory findings rather than being due to patient-reported outcomes.

⁴ Dabrafenib mesylate (GSK2118436B) has been associated with ocular toxicities including chorioretinitis, retinitis, iridocyclitis, iritis, and uveitis.

⁵ Edema limbs (peripheral edema) is a risk associated when dabrafenib mesylate (GSK2118436B) is used in combination with trametinib dimethyl sulfoxide (GSK1120212B) compared to dabrafenib mesylate (GSK2118436B) alone.

⁶ Fever (pyrexia) can be associated with hypotension and/or (in rare cases) syncope. The frequency of fever and serious febrile events is increased when dabrafenib mesylate (GSK2118436B) is used in combination with trametinib dimethyl sulfoxide (GSK1120212B).

⁷ Manifestations of allergic reactions (hypersensitivity) to dabrafenib mesylate (GSK2118436B) may include bullous rash (bullous dermatitis).

⁸ Squamous cell carcinoma (SCC), including SCC of the skin, SCC in situ (Bowen's disease), and keratoacanthoma have been observed.

⁹ New non-SCC malignancies have been reported including primary melanoma, basal cell carcinoma, and non-cutaneous malignancies.

¹⁰ Rash includes the terms: rash, rash acneiform, rash papular, rash maculo-papular, and erythema.

¹¹ Recurrent neutrophilic panniculitis has been observed in at least one patient treated with dabrafenib mesylate (GSK2118436B) in combination with the MEK inhibitor trametinib dimethyl sulfoxide (GSK1120212B).

¹² Venous thromboembolic events (including deep vein thrombosis and pulmonary embolism) is a risk associated when dabrafenib mesylate (GSK2118436B) is used in combination with trametinib dimethyl sulfoxide (GSK1120212B).

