5.4.3.4 Management and Dose Modification Guidelines for Hepatic Insufficiency

Cases of hepatic insufficiency have occurred in patient receiving dabrafenib and the combination of dabrafenib and trametinib. Prior to start of study treatment, concomitant medications should be reviewed for the potential risk of inducing hepatic toxicity and concomitant medications should be modified if clinically possible.

Table 8: Management and Dose Modification Guidelines for Hepatic Toxicity

Criteria –		Actions	Follow Up Assessments
ALT-absolute	ALT \geq 5xULN	Immediately discontinue dabrafenib, trametinib and HCQ/placebo	Viral hepatitis serology
ALT Increase	ALT \geq 3xULN persists for \geq 4 weeks	Report the event in CTEP-AERS within 7 calendar days.	Blood sample for pharmacokinetic (PK) analysis, obtained within 48 hours after last dose.
Bilirubin	ALT \geq 3xULN and bilirubin \geq 2xULN ($>$ 35% direct bilirubin)	Perform liver event follow up assessments.	Serum creatine phosphokinase (CPK) and lactate dehydrogenase (LDH). Fractionate bilirubin, if total bilirubin \geq 2xULN
INR	ALT \geq 3xULN and INR $>$ 1.5, if INR measured	Monitor the patient until liver chemistries resolve, stabilize, or return to within baseline (see MONITORING below). Do not restart/rechallenge	Obtain complete blood count with differential to assess

Criteria –		Actions	Follow Up Assessments

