Cannot Monitor	ALT \geq 3xULN and cannot be monitored weekly for 4 weeks	
patient with study treatment
 
If restart/rechallenge not allowed per protocol or not granted, permanently discontinue study treatment and may continue patient in the study for any protocol specified follow up assessments.
 
MONITORING:
 
For bilirubin or INR criteria:
 
Repeat liver chemistries (include ALT, AST, alkaline phosphatase, bilirubin) and perform liver event follow up assessments within 24 hrs.
 
A specialist or hepatology consultation is recommended.
 
Monitor patient twice weekly until liver chemistries resolve, stabilize or return to within baseline.
 
For All other criteria:
 
Repeat liver chemistries (include ALT, AST, alkaline phosphatase, bilirubin) and perform liver event follow up assessments within 24-72 hrs
 
Monitor patient weekly until liver chemistries resolve, stabilize or return to within baseline
	
eosinophilia
 
Record the appearance or worsening of clinical symptoms of liver injury, or hypersensitivity, on the AE report form.
 
Record use of concomitant medications on the concomitant medications report form including acetaminophen, herbal remedies, other over the counter medications.
 
Record alcohol use on the liver event alcohol intake case report form.
 
For bilirubin or INR criteria:
 
Anti-nuclear antibody, anti-smooth muscle antibody, Type 1 anti-liver kidney microsomal antibodies, and quantitative total immunoglobulin G (IgG or gamma globulins).
 
Serum acetaminophen adduct HPLC assay (quantifies potential acetaminophen contribution to liver injury in patients with definite or likely acetaminophen use in the preceding week).
 
Only in those with underlying chronic hepatitis B at study entry (identified by positive hepatitis B surface antigen): quantitative hepatitis B DNA and hepatitis delta antibody.
 
Liver imaging (ultrasound, magnetic resonance, or computerized tomography) and /or liver biopsy to evaluate liver disease: complete Liver Imaging and/or Liver Biopsy eCRF forms.

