5.4.3.12 New primary melanoma

New primary melanomas have been reported in patients treated with dabrafenib. These were identified within the first 5 months of therapy and did not require treatment modification other than excision. Monitoring for skin lesions should occur as described for cuSCC.

5.5 Drug interactions:

Table 16: Prohibited medications with CYP3A or CYP2C* Interactions

PROHIBITED – Strong inducers of CYP3A or CYP2C8, since concentrations of dabrafenib may be decreased	
Class	Drugs
Antibiotics	Rifamycin class agents (e.g., rifampin, rifabutin, rifapentine),
Anticonvulsant	Carbamazepine, oxcarbazepine, phenobarbital, phenytoin, s-mephentyoin
Miscellaneous	bosentan, St-John's wort

PROHIBITED – Strong inhibitors of CYP3A, or CYP2C8 since concentrations of dabrafenib may be increased	
Class/Therapeutic Area	Drugs/Agents
Antibiotics	Clarithromycin, telithromycin, troleandomycin
Antidepressant	Nefazodone
Antifungals	Itraconazole, ketoconazole, posaconazole, voriconazole
Hyperlipidemia	Gemfibrozil
Antiretroviral	ritonavir, saquinavir, atazanavir
Miscellaneous	Conivaptan

Table 17: USE WITH CAUTION: Moderate inhibitors of CYP3A, or CYP2C8 since concentrations of dabrafenib may be increased

Class/Therapeutic Area	Moderate CYP3A and CYP2C8 Inhibitors
Antiarrhythmics	Diltiazem, verapamil
Antibiotic	Erythromycin

Class/Therapeutic Area	Moderate CYP3A and CYP2C8 Inhibitors
Antifungal	Fluconazole
Miscellaneous	Aprepitant
USE WITH CAUTION: Co-administration of these drugs with study treatment may result in loss of efficacy. Monitor patient for loss of efficacy or substitute with another medication.	
Class/Therapeutic Area	CYP3A4, CYP2B6, CYP2C8, CYP2C9, CYP2C19 or Transporter Substrates that May be Affected by Induction
Analgesics	Alfentanil, buprenorphine, celecoxib, codeine, fentanyl, methadone, oxycodone
Antiarrhythmics	Disopyramide, dronedarone, mexiletine, propafenone, quinidine
Antibiotics	Chloramphenicol, doxycycline, erythromycin, moxifloxacin
Anticoagulants/ Antiplatelets	Cilostazole, warfarin
Anticonvulsants	Divalproex, lamotrigine, valproate, zonisamide
Antidepressants and Antipsychotics	Aripiprazole, bupropion, buspirone, desipramine, haloperidol, mirtazapine, pimozide, quetiapine, trazodone, amitriptyline, clomipramine, imipramine
Antidiabetics	Glyburide, saxagliptin, tolbutamide, nateglinide, pioglitazone, repaglinide, rosiglitazone
Antifungals	Caspofungin, fluconazole, terbinafine
Antihistamines	Astemizole, chlorpheniramine, ebastine

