8.1.12 Potential Drug Interactions

In vivo data shows that metabolism of dabrafenib mesylate and its metabolites is mediated by CYP3A4 and CYP2C8 with minor contributions by CYP 2C9 and 2C19. Use caution if strong inducers or inhibitors of CYP2C8 or 3A4 are co-administered with dabrafenib. Although *in vitro* studies indicate dabrafenib mesylate and its metabolites are substrates for P-glycoprotein (P-gp) and BCRP transporters, the apparent high oral bioavailability and permeability indicate modulation of efflux transporters will have minimal impact on dabrafenib pharmacokinetics.

Dabrafenib mesylate and its metabolites showed moderate inhibition of CYP 2C8, 2C9, 2C19 and 3A4 in human liver microsomes. Use caution in patients who are taking sensitive substrates of these enzymes. Additionally, dabrafenib and its metabolites showed inhibition of OATP1B1, OATP1B3, OAT1, OAT3 and OCT2 transporter systems; however, the drug-drug interaction risk is believed to be low based on clinical exposures.

Neither dabrafenib nor its metabolites show inhibition of P-gp *in vitro*, but are moderate inhibitors of BCRP. Dabrafenib may affect the pharmacokinetics of co-medications with narrow therapeutic index whose absorption or clearance depends on BCRP-mediated transport.

In vitro, dabrafenib mesylate induces CYP 2B6 and 3A4 and possibly CYP 2C8, 2C9 2C19, UDP glucuronosyltransferase and P-gp.; although *in vivo*, the overall effect of dabrafenib induction is as a mild inducer of CYP2C9 and moderate inducer of CYP3A4. Use caution in patients who are taking substrates of these pathways, such as warfarin or hormonal contraceptives and monitor for loss of efficacy.

Dabrafenib solubility is pH-dependent but is not expected to be reduced when co-administered with pH elevating agents like proton pump inhibitors.

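### Section 5.2.8 exempts anticoagulated patients from the liver INR criterion, but the INR row of Table 8 (Section 5.4.3.4) does not

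*Combined protocol and SAP*

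**What the plan says.** Two places in the protocol set liver thresholds.

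- **Section 5.2.8 (Liver Chemistry Changes)** gives five criteria, each reportable through CTEP-AERS within 7 calendar days. The INR criterion is ALT at or above 3xULN with INR at or above 1.5, if measured, with the qualification "INR threshold does not apply if patient is on anticoagulant". The section then sends sites to the dose-modification instructions for management.
- **Section 5.4.3.4, Table 8** has five rows: ALT-absolute, ALT Increase, Bilirubin, INR and Cannot Monitor. The INR row reads "ALT \geq 3xULN and INR $>$ 1.5, if INR measured" and does not mention anticoagulants. The Actions column includes "Immediately discontinue dabrafenib, trametinib and HCQ/placebo" and "Report the event in CTEP-AERS within 7 calendar days".

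Patients on anticoagulants can be in the trial. The drug-interaction tables in Section 5.5 place "Cilostazole, warfarin" under use with caution, not under prohibited drugs. Section 8.1.12 asks for care with drugs "such as warfarin or hormonal contraceptives". Footnote 12 in Section 5.3.1 adds a reason why anticoagulation may begin on study: "Venous thromboembolic events (including deep vein thrombosis and pulmonary embolism) is a risk associated" with the dabrafenib and trametinib combination. Section 3.1.18.3 also admits patients with controlled atrial fibrillation.

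**The concern.** An INR raised by an anticoagulant says little about liver function, which is presumably why Section 5.2.8 excludes it. Table 8 uses almost the same criterion without that exclusion and attaches heavier consequences. A site following Table 8 literally would file a report that 5.2.8 does not ask for. More importantly, it would withdraw standard dabrafenib and trametinib, together with the blinded agent, because of an INR that the anticoagulant was meant to raise. Table 8 also tells sites not to restart, so the loss of therapy could be permanent.

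**Working it through.** The plan gives no figure to reproduce. The check is a comparison of the two texts, followed by test cases.

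**Step 1. The INR criterion in the two places**

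| | Section 5.2.8 | Table 8, INR row |
|---|---|---|
| ALT | at or above 3xULN | at or above 3xULN |
| INR, if measured | at or above 1.5 | above 1.5 |
| On an anticoagulant | criterion does not apply | no exemption |
| Consequence | report within 7 days | depends on how the Actions column is read (step 2) |

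**Step 2. Does the Actions text reach the INR row?** The table is broken in the available text, so this is an inference. The evidence for one common cell is:

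- The sentence forbidding restart begins beside the INR row and finishes beside the Cannot Monitor row, so the text runs across row boundaries.
- The monitoring instructions in the same column have one part for the bilirubin and INR criteria and another for all other criteria. They were therefore written for every row.
- Read line by line, the column gives odd results. ALT at or above 5xULN would lead to a stop with no report, although 5.2.8 makes ALT above 5xULN reportable. The bilirubin row would lead only to follow-up assessments.

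On the common-cell reading, the INR row carries both the 7-day report and the three-drug stop. On a line-by-line reading it carries neither.

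**Step 3. Could an exemption have been lost in extraction?** This cannot be fully excluded. However, the footnotes to Tables 7, 10, 11 and 12 survived, and Table 8 shows neither a marker nor a note.

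**Step 4. Test cases on the common-cell reading.** INR is 2.5 and there is no other trigger: no bilirubin criterion, no liver symptoms, under 4 weeks' duration, and weekly monitoring possible. The values are illustrative and are not rates.

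| ALT (xULN) | Anticoagulant | Section 5.2.8 | Table 8 |
|---|---|---|---|
| 2.9 | yes | no report | no row met |
| 3.5, 4.0, 4.9 | yes | no report | INR row: report and stop |
| 3.5, 4.0, 4.9 | no | report | INR row: report and stop |
| 5.1, 6.0 | yes | report (ALT criterion) | report and stop (ALT row) |

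The disagreement is confined to ALT at or above 3x and below 5xULN, INR above 1.5, on an anticoagulant, with no other trigger. Without the anticoagulant the two lists agree in the same ALT range, so the missing exemption is what separates them.

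**The case against.** **Section 5.2.8 governs reporting.** Section 5.2.5 says that the instructions following it were tailored to this trial and set out its expedited reporting requirements. Table 8 is a management table. A site therefore has a designated source for reporting, and following Table 8 instead costs at most one extra report. This stands for the reporting half. It does not settle whether an anticoagulated patient should stop treatment.

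**A stopping rule may differ from a reporting rule.** Table 8 could have left the exemption out on purpose. The documents do not say. But no reason is given for stopping three drugs on an INR judged uninformative for reporting, and Table 8 itself contains the reporting duty.

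**The report does not stand on firmer ground than the stop.** A reader might infer that the reporting conflict holds however the table is read. It does not. Both instructions come from the same broken Actions text, and without the common-cell reading the INR row orders neither.

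**Symptomatic ALT elevation.** Section 5.2.8 makes ALT above 3xULN with symptoms of liver injury or hypersensitivity reportable and refers sites to dose modification, yet Table 8 has no row for it. A reader might infer that these patients have no guidance, or that an immediate three-drug stop was omitted by mistake. The documents support neither inference:

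- Section 5.4.1.1 modifies dabrafenib and trametinib together for treatment-related toxicity.
- Section 5.4.1.2 holds HCQ/placebo at grade 3 or above.
- Section 5.4.1.3 reduces HCQ/placebo first for overlapping toxicities, then the doublet.
- Table 4 in Section 5.4.2 covers toxicity attributed only to dabrafenib and/or trametinib.
- Section 5.7 ends therapy for unacceptable toxicity.

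Which grade-based rule applies cannot be fixed from the documents, because they do not give the ALT grade limits. A mandatory stop would also have a cost: Section 3.1.26 admits patients with ALT up to 3.0xULN, so a trivial rise with symptoms could end standard therapy.

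**Rechallenge and operators.** Table 8 forbids restarting, then says "If restart/rechallenge not allowed per protocol or not granted, permanently discontinue study treatment". A reader might see a contradiction. Since no route for granting rechallenge is described, both sentences lead to permanent discontinuation. This wording, and the small differences in inequality signs between the lists, merit clarification only.

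**Conclusion.** The inconsistency is real and small. Section 5.2.8 exempts anticoagulated patients from the liver INR criterion and Table 8 does not. On the common-cell reading, a patient in the window found above must be reported and stopped on all three agents for an INR that 5.2.8 disregards. The conclusion rests on that reading for both the report and the stop, and on no exemption having been lost from Table 8 in extraction. How many patients would fall in the window cannot be derived from the documents.

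The missing row for symptomatic ALT is a secondary matter for the sponsor's clinical judgement and is not an error in the plan.

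This is a minor safety-consistency correction. The primary analysis is unaffected: the PFS definition in Section 9.2 and the comparison in Section 9.4 do not refer to liver criteria, and Section 5.8 follows patients who stop early until progression.

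**What to change.** Add the words "INR threshold does not apply if patient is on anticoagulant" to the INR row of Table 8, matching Section 5.2.8. If the sponsor does want anticoagulated patients stopped on this criterion, Table 8 should say so and give the reason.

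Optionally, in the same amendment, state the intended action for ALT above 3xULN with new or worsening liver symptoms, without presuming a mandatory three-drug stop. The inequality signs and the rechallenge sentence could be tidied at the same time.

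The main change is one clause of protocol wording. It alters no visits, sample size or analysis. Any new action for symptomatic ALT would be a treatment rule and needs clinical review first.

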5.2.9 Other recipients of adverse event reports and supplemental data

A drug supporter representative may call a site for additional or supplemental information regarding a serious adverse event. Any additional written AE information requested by the drug supporter MUST be submitted to BOTH ECOG-ACRIN and the drug supporter.

Adverse events determined to require expedited reporting must also be reported by the institution, according to the local policy and procedures, to the Institutional Review Board responsible for oversight of the patient.

5.2.10 Second Primary Cancer Reporting Requirements

All cases of second primary cancers, including acute myeloid leukemia (AML) and myelodysplastic syndrome (MDS), that occur following treatment on NCI-sponsored trials must be reported to ECOG-ACRIN using Medidata Rave.

- **A second malignancy is a cancer that is UNRELATED to any prior anti-cancer treatment (including the treatment on this protocol). Second malignancies require ONLY routine reporting as follows:**
 1. Complete a Second Primary Form in Medidata Rave within 14 days.
 2. Upload a copy of the pathology report to ECOG-ACRIN via Medidata Rave confirming the diagnosis.

3. If the patient has been diagnosed with AML/MDS, upload a copy of the cytogenetics report (if available) to ECOG-ACRIN via Medidata Rave.
- **A secondary malignancy is a cancer CAUSED BY any prior anti-cancer treatment (including the treatment on this protocol). Secondary malignancies require both routine and expedited reporting as follows:**
 1. Complete a Second Primary Form in Medidata Rave within 14 days.
 2. Report the diagnosis via CTEP-AERS at <http://ctep.cancer.gov>.
Report under a.) leukemia secondary to oncology chemotherapy, b.) myelodysplastic syndrome, or c.) treatment related secondary malignancy
 3. Upload a copy of the pathology report to ECOG-ACRIN via Medidata Rave and submit a copy to NCI/CTEP confirming the diagnosis.
 4. If the patient has been diagnosed with AML/MDS, upload a copy of the cytogenetics report (if available) to ECOG-ACRIN via Medidata Rave and submit a copy to NCI/CTEP.

NOTE: The ECOG-ACRIN Second Primary Form and the CTEP-AERS report should not be used to report recurrence or development of metastatic disease.

NOTE: If a patient has been enrolled in more than one NCI-sponsored study, the ECOG-ACRIN Second Primary Form must be submitted for the most recent trial. ECOG-ACRIN must be provided with a copy of the form and the associated pathology report and cytogenetics report (if available) even if ECOG-ACRIN was not the patient's most recent trial.

NOTE: Once data regarding survival and remission status are no longer required by the protocol, no follow-up data should be submitted in CTEP-AERS or by the ECOG-ACRIN Second Primary Form.

5.3 Comprehensive Adverse Events and Potential Risks lists (CAEPR)

5.3.1 Comprehensive Adverse Events and Potential Risks list (CAEPR) for Dabrafenib NSC763760

The Comprehensive Adverse Events and Potential Risks list (CAEPR) provides a single list of reported and/or potential adverse events (AE) associated with an agent using a uniform presentation of events by body system. Frequency is provided based on 1374 patients. Below is the CAEPR for Dabrafenib

Version 2.5, September 30, 2019¹

Adverse Events with Possible Relationship to Dabrafenib (GSK2118436B) (CTCAE 5.0 Term) [n= 1374]		
Likely (>20%)	Less Likely (<=20%)	Rare but Serious (<3%)
BLOOD AND LYMPHATIC SYSTEM DISORDERS		
	Anemia ^{2,3}	
EYE DISORDERS		
		Eye disorders - Other (iritis) ⁴
		Uveitis ⁴
GASTROINTESTINAL DISORDERS		
	Abdominal pain	
		Colitis
		Colonic perforation
	Constipation	
	Diarrhea	
Nausea		
		Pancreatitis
	Vomiting	
GENERAL DISORDERS AND ADMINISTRATION SITE CONDITIONS		
	Chills	
	Edema limbs ⁵	
Fatigue		
Fever ⁶		
	Flu like symptoms	
IMMUNE SYSTEM DISORDERS		
		Allergic reaction ⁷
INFECTIONS AND INFESTATIONS		
	Upper respiratory infection	
INVESTIGATIONS		
	Creatinine increased ³	
	Neutrophil count decreased ³	
	Platelet count decreased ³	
	White blood cell decreased ³	
METABOLISM AND NUTRITION DISORDERS		
	Anorexia	
	Hyperglycemia ³	
	Hypokalemia ³	
	Hyponatremia ³	

Adverse Events with Possible Relationship to Dabrafenib (GSK2118436B) (CTCAE 5.0 Term) [n= 1374]		
Likely (>20%)	Less Likely (<=20%)	Rare but Serious (<3%)
	Hypophosphatemia ³	
MUSCULOSKELETAL AND CONNECTIVE TISSUE DISORDERS		
Arthralgia		
	Back pain	
	Myalgia	
	Pain in extremity	
NEOPLASMS BENIGN, MALIGNANT AND UNSPECIFIED (INCL CYSTS AND POLYPS)		
	Neoplasms benign, malignant and unspecified (incl cysts and polyps) - Other (squamous cell carcinoma or keratoacanthoma) ⁸	
	Skin papilloma	
		Treatment related secondary malignancy (non-SCC) ⁹
NERVOUS SYSTEM DISORDERS		
	Dizziness	
Headache		
		Syncope
RENAL AND URINARY DISORDERS		
		Acute kidney injury
RESPIRATORY, THORACIC AND MEDIASTINAL DISORDERS		
	Cough	
SKIN AND SUBCUTANEOUS TISSUE DISORDERS		
Alopecia		
	Dry skin	
	Hair texture abnormal	
	Hyperhidrosis	
Hyperkeratosis		
	Palmar-plantar erythrodysesthesia syndrome	
	Pruritus	
Rash ¹⁰		
		Skin and subcutaneous tissue disorders - Other (drug reaction with eosinophilia and systemic symptoms [DRESS])
		Skin and subcutaneous tissue disorders - Other (neutrophilic panniculitis) ¹¹
		Stevens-Johnson syndrome
VASCULAR DISORDERS		
	Hypertension	
	Thromboembolic event ¹²	
	Vascular disorders - Other (hemorrhage) ¹³	

¹ This table will be updated as the toxicity profile of the agent is revised. Updates will be distributed to all Principal Investigators at the time of revision. The current version can be obtained by contacting [contact]. Your name, the name of the investigator, the protocol and the agent should be included in the e-mail.

² The incidence of anemia is increased when dabrafenib mesylate (GSK2118436B) is used in combination with trametinib dimethyl sulfoxide (GSK1120212B).

³ The frequencies of these events are based upon laboratory findings rather than being due to patient-reported outcomes.

⁴ Dabrafenib mesylate (GSK2118436B) has been associated with ocular toxicities including chorioretinitis, retinitis, iridocyclitis, iritis, and uveitis.

⁵ Edema limbs (peripheral edema) is a risk associated when dabrafenib mesylate (GSK2118436B) is used in combination with trametinib dimethyl sulfoxide (GSK1120212B) compared to dabrafenib mesylate (GSK2118436B) alone.

⁶ Fever (pyrexia) can be associated with hypotension and/or (in rare cases) syncope. The frequency of fever and serious febrile events is increased when dabrafenib mesylate (GSK2118436B) is used in combination with trametinib dimethyl sulfoxide (GSK1120212B).

⁷ Manifestations of allergic reactions (hypersensitivity) to dabrafenib mesylate (GSK2118436B) may include bullous rash (bullous dermatitis).

⁸ Squamous cell carcinoma (SCC), including SCC of the skin, SCC in situ (Bowen's disease), and keratoacanthoma have been observed.

⁹ New non-SCC malignancies have been reported including primary melanoma, basal cell carcinoma, and non-cutaneous malignancies.

¹⁰ Rash includes the terms: rash, rash acneiform, rash papular, rash maculo-papular, and erythema.

¹¹ Recurrent neutrophilic panniculitis has been observed in at least one patient treated with dabrafenib mesylate (GSK2118436B) in combination with the MEK inhibitor trametinib dimethyl sulfoxide (GSK1120212B).

¹² Venous thromboembolic events (including deep vein thrombosis and pulmonary embolism) is a risk associated when dabrafenib mesylate (GSK2118436B) is used in combination with trametinib dimethyl sulfoxide (GSK1120212B).

¹³ Treatment with dabrafenib mesylate (GSK2118436B) in combination with trametinib dimethyl sulfoxide (GSK1120212B) resulted in an increased incidence and severity of hemorrhagic events compared to patients treated with dabrafenib mesylate (GSK2118436B) as a single agent. Sites of hemorrhage may include, but are not limited to, intracranial, reproductive tract, respiratory tract, and gastrointestinal hemorrhage.

Adverse events reported on Dabrafenib mesylate (GSK2118436B) trials, but for which there is insufficient evidence to suggest that there was a reasonable possibility that Dabrafenib mesylate (GSK2118436B) caused the adverse event:

BLOOD AND LYMPHATIC SYSTEM DISORDERS - Blood and lymphatic system disorders - Other (agranulocytosis); Blood and lymphatic system disorders - Other (pancytopenia); Disseminated intravascular coagulation; Febrile neutropenia; Hemolysis; Leukocytosis

CARDIAC DISORDERS - Atrial fibrillation; Atrial flutter; Chest pain - cardiac; Heart failure; Left ventricular systolic dysfunction; Mitral valve disease; Myocardial infarction; Pericardial effusion; Sinus tachycardia

EAR AND LABYRINTH DISORDERS - Ear pain

ENDOCRINE DISORDERS - Hyperthyroidism; Hypothyroidism

EYE DISORDERS - Blurred vision; Eye disorders - Other (amaurosis fugax); Eye disorders - Other (vitreous detachment); Floaters; Photophobia; Retinal detachment; Retinopathy; Vision decreased

GASTROINTESTINAL DISORDERS - Dry mouth; Dyspepsia; Gastritis; Stomach pain

GENERAL DISORDERS AND ADMINISTRATION SITE CONDITIONS - Death NOS; Disease progression; Gait disturbance; Localized edema; Malaise; Non-cardiac chest pain; Pain

HEPATOBILIARY DISORDERS - Cholecystitis; Hepatic pain

INFECTIONS AND INFESTATIONS - Bacteremia; Bronchial infection; Catheter related infection; Device related infection; Gallbladder infection; Infections and infestations - Other (bacterial peritonitis); Infections and infestations - Other (blood culture positive); Infections and infestations - Other (croup infectious); Infections and infestations - Other (Epstein-Barr virus infection); Infections and infestations - Other (respiratory tract infection); Lung infection; Otitis media; Pharyngitis; Rash pustular; Rhinitis infective; Sepsis; Skin infection; Urinary tract infection; Viremia

INJURY, POISONING AND PROCEDURAL COMPLICATIONS - Bruising; Injury, poisoning and procedural complications - Other (complication associated with device); Injury, poisoning and procedural complications - Other (device occlusion); Injury, poisoning and procedural complications - Other (radiation injury, stroke-like migraine attacks after radiation therapy); Seroma

INVESTIGATIONS - Alanine aminotransferase increased; Alkaline phosphatase increased; Aspartate aminotransferase increased; Blood bilirubin increased; CD4 lymphocytes decreased; Ejection fraction decreased; Electrocardiogram QT corrected interval prolonged; GGT increased; Lipase increased; Lymphocyte count decreased; Weight gain; Weight loss

METABOLISM AND NUTRITION DISORDERS - Dehydration; Hypercalcemia; Hyperkalemia; Hypernatremia; Hyperuricemia; Hypocalcemia; Hypoglycemia; Hypomagnesemia

MUSCULOSKELETAL AND CONNECTIVE TISSUE DISORDERS - Arthritis; Generalized muscle weakness; Muscle cramp; Muscle weakness lower limb; Muscle weakness upper limb; Neck pain

NEOPLASMS BENIGN, MALIGNANT AND UNSPECIFIED (INCL CYSTS AND POLYPS) - Leukemia secondary to oncology chemotherapy; Myelodysplastic syndrome; Neoplasms benign, malignant and unspecified (incl cysts and polyps) - Other (acrochordon); Neoplasms benign, malignant and unspecified (incl cysts and polyps) - Other (bile duct adenocarcinoma); Neoplasms benign, malignant and unspecified (incl cysts and polyps) - Other (mycosis fungoides)

NERVOUS SYSTEM DISORDERS - Ataxia; Cognitive disturbance; Depressed level of consciousness; Dysgeusia; Dysphasia; Hydrocephalus; Lethargy; Nervous system disorders - Other (expressive aphasia); Nervous system disorders - Other (intracranial pressure increased); Paresthesia; Seizure; Somnolence; Stroke

PSYCHIATRIC DISORDERS - Agitation; Anxiety; Confusion; Depression; Hallucinations; Insomnia

RENAL AND URINARY DISORDERS - Proteinuria; Renal calculi; Urinary frequency; Urinary retention

REPRODUCTIVE SYSTEM AND BREAST DISORDERS - Menorrhagia; Prostatic obstruction; Reproductive system and breast disorders - Other (hematospermia)

RESPIRATORY, THORACIC AND MEDIASTINAL DISORDERS - Adult respiratory distress syndrome; Allergic rhinitis; Dyspnea; Hypoxia; Nasal congestion; Oropharyngeal pain; Pleuritic pain; Productive cough; Pulmonary edema; Respiratory failure; Rhinorrhea; Sore throat; Stridor; Voice alteration

SKIN AND SUBCUTANEOUS TISSUE DISORDERS - Bullous dermatitis⁷; Eczema; Erythroderma; Photosensitivity; Purpura; Skin and subcutaneous tissue disorders - Other (palmoplantar keratoderma); Skin and subcutaneous tissue disorders - Other (sunburn); Skin hyperpigmentation

VASCULAR DISORDERS - Flushing; Hot flashes; Hypotension

NOTE: Dabrafenib (GSK2118436B) in combination with other agents could cause an exacerbation of any adverse event currently known to be caused by the other agent, or the combination may result in events never previously associated with either agent.

5.3.2 Comprehensive Adverse Events and Potential Risks list (CAEPR) for Trametinib dimethyl sulfoxide (GSK1120212B, NSC 763093)

The Comprehensive Adverse Events and Potential Risks list (CAEPR) provides a single list of reported and/or potential adverse events (AE) associated with an agent using a uniform presentation of events by body system. Frequency is provided based on 1111 patients. Below is the CAEPR for Trametinib (GSK1120212B).

Version 2.6, October 10, 2019¹

Adverse Events with Possible Relationship to Trametinib (GSK1120212B) (CTCAE 5.0 Term) [n= 1111]		
Likely (>20%)	Less Likely (<=20%)	Rare but Serious (<3%)
BLOOD AND LYMPHATIC SYSTEM DISORDERS		
	Anemia	
CARDIAC DISORDERS		
		Heart failure
		Left ventricular systolic dysfunction
	Sinus bradycardia	
EYE DISORDERS		
	Blurred vision	
	Dry eye	
		Eye disorders - Other (chorioretinopathy also known as retinal pigment epithelial detachment)
		Eye disorders - Other (retinal vein occlusion)
	Eye disorders - Other (visual disorders) ²	
		Papilledema
	Periorbital edema	
GASTROINTESTINAL DISORDERS		
	Abdominal pain	
		Colitis
		Colonic perforation
	Constipation	
Diarrhea		
	Dry mouth	
	Dyspepsia	
	Mucositis oral	
Nausea		
	Vomiting	
GENERAL DISORDERS AND ADMINISTRATION SITE CONDITIONS		
	Chills	

Adverse Events with Possible Relationship to Trametinib (GSK1120212B) (CTCAE 5.0 Term) [n= 1111]		
Likely (>20%)	Less Likely (<=20%)	Rare but Serious (<3%)
	Edema face	
Fatigue	Fever	
Generalized edema ³		
IMMUNE SYSTEM DISORDERS		
	Allergic reaction ⁴	
INFECTIONS AND INFESTATIONS		
	Folliculitis	
	Lung infection	
	Paronychia	
	Skin infection	
INVESTIGATIONS		
	Alanine aminotransferase increased	
	Alkaline phosphatase increased	
	Aspartate aminotransferase increased	
	CPK increased	
	Ejection fraction decreased	
METABOLISM AND NUTRITION DISORDERS		
	Anorexia	
	Dehydration	
	Hypoalbuminemia	
	Hypomagnesemia	
	Hyponatremia	
MUSCULOSKELETAL AND CONNECTIVE TISSUE DISORDERS		
	Arthralgia	
	Back pain	
	Pain in extremity	
		Rhabdomyolysis
NERVOUS SYSTEM DISORDERS		
	Dizziness	
	Headache	
RESPIRATORY, THORACIC AND MEDIASTINAL DISORDERS		
	Cough	
	Dyspnea	
		Pneumonitis
SKIN AND SUBCUTANEOUS TISSUE DISORDERS		
	Alopecia	
	Dry skin	
	Nail changes	
		Palmar-plantar erythrodysesthesia syndrome
	Pruritus	

Adverse Events with Possible Relationship to Trametinib (GSK1120212B) (CTCAE 5.0 Term) [n= 1111]		
Likely (>20%)	Less Likely (<=20%)	Rare but Serious (<3%)
		Skin and subcutaneous tissue disorders - Other (drug reaction with eosinophilia and systemic symptoms [DRESS])
Skin and subcutaneous tissue disorders - Other (rash) ⁵		Stevens-Johnson syndrome ⁶
VASCULAR DISORDERS		
	Hypertension	
		Thromboembolic event (venous)
	Vascular disorders - Other (hemorrhage) ⁷	

¹ This table will be updated as the toxicity profile of the agent is revised. Updates will be distributed to all Principal Investigators at the time of revision. The current version can be obtained by contacting [contact]. Your name, the name of the investigator, the protocol and the agent should be included in the e-mail.

² Visual disorders include visual disturbance that can be associated with conjunctival hemorrhage, corneal graft rejection, cyclitis, eye nevus, halo vision, iritis, macular edema, retinal hemorrhage, visual acuity reduced, visual impairment, and vitreous detachment.

³ Generalized edema includes edema, lymphedema, and edema limbs.

⁴ Hypersensitivity (allergic reactions) may present with symptoms such as fever, rash, increased liver function tests, and visual disturbances.

⁵ Skin and subcutaneous tissue disorders - Other (rash) may include rash, rosacea, erythematous rash, genital rash, rash macular, exfoliative rash, rash generalized, erythema, rash papular, seborrheic dermatitis, dermatitis psoriasiform, rash follicular, skin fissures, and skin chapped.

⁶ Stevens-Johnson syndrome has been observed in patients treated with trametinib and dabrafenib combination.

⁷ The majority of hemorrhage events were mild. Major events, defined as symptomatic bleeding in a critical area or organ (e.g., eye, GI hemorrhage, GU hemorrhage, respiratory hemorrhage), and fatal intracranial hemorrhages have been reported.

